#### **10.2.3 Demographics/Medical and Surgical History**

Demographic information per country regulations (age, full date of birth, gender, race, and ethnicity), along with medical and surgical history, will be obtained and recorded in the eCRF at Visit 1.

Medical and surgical history will be entered in the eCRF at Visit 1. This includes date of diagnosis of PFIC, prior investigational medications for PFIC, historical (3 months prior to Screening) LFT values (AST, ALT, and total bilirubin), ongoing medication, any surgery performed, any other diagnosis, and historical biopsy data.

If a liver biopsy has been performed within 1 year prior to Screening, or during the study, the results will be recorded in the eCRF.

#### **10.2.4 Clinical Genetic Testing**

If confirmatory clinical genetic testing for PFIC Type 1 or 2 has been performed prior to Screening Visit 1, the confirmatory clinical genetic testing laboratory report will be verified by a central reader to determine eligibility.

Regardless of previous genetic testing, a blood sample will be drawn at Visit 1 for all patients for DNA extraction. Genetic testing will only be performed on a patient's extracted DNA if the previous clinical genetic result is equivocal, unavailable, or unobtainable. In such cases, screening for pathologic biallelic variations in the *ATP8B1* or *ABCB11* genes will be performed if patient meets remaining inclusion and exclusion criteria and only after sponsor case review. No other diagnostic genetic testing will be offered.

#### **10.2.5 Physical Examination**

A physician or suitably trained qualified assistant will perform a complete physical examination, including voluntary photography, at Visits 1, 3, and 9. A skin examination will be conducted at Visits 1, 3, 4, 6, 9, and 10 (see [Table 1](#)).

A complete physical examination will include assessment of general appearance, eyes, ears, nose, throat, head/neck/thyroid, lymph nodes, cardiovascular, lungs/chest, abdomen, genitourinary, extremities, skin, musculoskeletal, neurologic, and other.

Skin will be examined thoroughly and excoriations/scratch marks recorded.

### **10.2.6 Vital Signs**

Evaluation of vital signs will be performed at all visits. This includes blood pressure (systolic and diastolic), pulse, respiratory rate, temperature, height (or length depending on age), and body weight (using a certified weight scale) at clinic visits. BMI will be calculated.

### **10.2.7 Abdominal Ultrasound**

Ultrasound of the liver and spleen will be performed at randomization (Visit 3) and at EOT (Visit 9). Liver size, echogenicity, and presence of masses/nodules as well as spleen size will be recorded.

### **10.2.8 Overdose**

A4250 is minimally absorbed and has a very low systemic availability. Based on toxicology data, for study purposes any dose exceeding a total of >3 mg/kg body weight of A4250 taken as a single dose or as a cumulative dose within 24 hours is defined as an overdose.

The no-adverse-effect dose level in the most sensitive species (defined as 20 mg/kg/day) in the rat 1 month toxicity study gives a human equivalent dose of approximately 194 mg/day in a 60 kg person. This dose is approximately 10-fold higher than the maximum possible dose predicted in human studies (20 mg).

The investigator/investigative staff should immediately and not later than within 24 hours of knowledge of the overdose, be reported by the investigator or delegate on the SAE report form. In the event of an A4250 overdose, the patient should be monitored closely.

### **10.2.9 Pregnancy**

If a pregnancy is discovered in a female patient enrolled in the study before the end of dosing, the patient will be immediately discontinued from the study and will attend the same visits as a prematurely withdrawn patient. If the pregnancy is discovered in a female patient enrolled in the study after the end of dosing, the patient will continue in the study per protocol. If a pregnancy occurs in a male patient's partner at any time during the study, the pregnancy should also be reported and followed.

Pregnancy is not considered to be an AE. However, if the patient has been dosed with the study drug, the pregnancy must be reported on the Paper Pregnancy Notification Form immediately within 24 hours after recognition to Albireo/Safety Manager (please refer to [Section 10.1.3](#)). Date of exposure and as far as possible, details of the period of gestation at the time of exposure must be given.

The pregnancy should be followed to determine outcome, including spontaneous termination, details of birth, and presence of any birth defects, congenital anomalies or newborn or maternal complication. The infant who was exposed in-utero will be followed for up to 2 years after delivery. Individual cases with an abnormal outcome in association with the study drug should be reported on an expedited basis, i.e., reported rapidly to a competent authority.

## 11 STATISTICAL EVALUATION

All personnel involved with the analysis of the study will remain blinded until database lock for the double-blind Treatment Period and until major protocol violations have been identified.

All statistical analyses will be performed using SAS version 9.3 or higher.

### 11.1 Sample Size and Power

For the EU and RoW, the primary analysis will relate to the bile acid responder endpoint (at the 1-sided 1.25% level). For the US, the primary analysis will relate to the pruritus endpoint (at the 1-sided 1.25% level). The aim is to enroll 60 to 70 patients in order to get at least 60 evaluable patients.

Assuming 60% responders (patients experiencing at least 70% reduction in fasting s-BA concentration or reaching  $\leq 70$   $\mu\text{mol/L}$ ) in the A4250 dose group and 10% responders in the placebo group, approximately 20 patients per group are required to achieve a power of 84% with a 1.25% 1-sided Type-1 error.

For pruritus, with approximately 20 patients per treatment group, the power is 83% given an assumed treatment effect difference of -1.0 in change from baseline (-1.6 for A4250 and -0.6 for placebo) on the Albireo ObsRO scratching score with a SD of 0.95 and a Type I error of 1.25% (1-sided).

### 11.2 Statistical Methods

#### 11.2.1 Statistical Analysis Sets

##### **Safety Analysis Set**

The safety analysis set will consist of all patients who received at least 1 dose of study drug. Patients will be analyzed according to the treatment they actually received. The safety analysis set will be the primary analysis set for safety analyses.

##### **Full Analysis Set**

The full analysis set (FAS) will consist of all randomized patients who received at least 1 dose of assigned treatment. Patients will be analyzed in the treatment group they were randomized to even if they received incorrect study drug. The FAS will be the primary analysis set for efficacy analyses.

##### **Per Protocol Analysis Set**

The per protocol (PP) analysis set is a subset of the FAS, and will consist of all randomized patients for whom no major protocol violation (no violation which may affect the study efficacy outcome) is documented. The PP analysis set will provide supportive data for the efficacy analyses.

Allocation of patients to the PP analysis set will be performed before unblinding of the study.

## 11.2.2 Methods of Statistical Analyses

### 11.2.2.1 General Principles

[figure not shown]
The primary objective of this study is to show superiority in efficacy of A4250 (120 µg/kg/day and 40 µg/kg/day) compared to placebo in patients with PFIC Types 1 and 2.

In the EU and RoW, for the primary efficacy variable fasting bile acid responder endpoint (at least a 70% reduction in fasting s-BA concentration or reaching a level  $\leq 70$  µmol/L at the end of treatment), the null hypothesis will be tested against the alternative hypothesis ( $\alpha = 0.0125$ , 1-sided).

The test will be performed at a Type I error rate of  $\leq 0.0125$  1-sided, as described above, based on the least squares means of the treatment difference in mean probability scale.

To strictly control overall Type I error rate across the dose groups and also across the primary and the main secondary endpoint to a 1-sided 2.5% level, a Bonferroni-based parallel gate-keeping procedure will be used. In this procedure the total significance level of 2.5% (1-sided) will be split equally between the dose groups. Only a dose group that is significant for the primary endpoint will be tested, at the nominal significance level of 1.25% (1-sided), for the main secondary endpoint (here the pruritus endpoint). If the previous step was not successful, the analysis of the following step will be considered descriptive. If the procedure reaches the secondary endpoint for both dose groups, these will be evaluated using the Bonferroni Holm procedure. The multiple comparison procedure is presented in [Figure 2](#).

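### The gatekeeping scheme never returns a winning dose's 1.25% to the other dose's primary test, giving up about 7 points of both-dose power for no gain in error control

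*Protocol*

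**What the plan says.** Section 11.2.2.1 (General Principles) sets out the EU/RoW scheme, with bile acid response as primary and pruritus as main secondary, and repeats it for the US with the two endpoints exchanged.

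- **Split.** "In this procedure the total significance level of 2.5% (1-sided) will be split equally between the dose groups". Each primary test is set at a one-sided level of at most 0.0125, and no higher level is given anywhere for a primary.
- **From primary to secondary.** "Only a dose group that is significant for the primary endpoint will be tested, at the nominal significance level of 1.25% (1-sided"), for its main secondary endpoint. The step stays within the dose.
- **Between doses.** "If the procedure reaches the secondary endpoint for both dose groups, these will be evaluated using the Bonferroni Holm procedure". This is the only transfer between doses in the text.
- **Power.** Section 11.1 gives, for the responder endpoint, "Assuming 60% responders" on active and "10% responders in the placebo group, approximately 20 patients per group are required to achieve a power of 84"%. For pruritus, "the power is 83% given an assumed treatment effect difference of -1.0 in change from baseline", "with a SD of 0.95 and a Type I error of 1.25% (1-sided"). Both powers are for one dose against placebo; no both-dose power is stated.

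The text refers to Figure 2 for the procedure. That figure is not visible in the copy reviewed.

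**The concern.** The Holm step needs both primaries to have been won already. Suppose one dose wins its primary and its main secondary, and the other has a one-sided primary p-value of 0.02. The first dose's 1.25% has then done its work and could be reused, but the text gives it nowhere to go. The second dose is judged at 1.25% and fails, although testing it at 2.5% at that point would keep the familywise error at 2.5%.

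The stated objective is superiority of both doses over placebo, with about 20 patients per arm in a rare disease. Power that can be had by rewording a rule is worth taking. The protocol already accepts recycling on the secondary endpoint; it lacks it on the primary, where a failure costs most.

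**Working it through.** **1. Reproduce the protocol's powers** (20 per group, one-sided 1.25%).

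- Responders, 60% vs 10%, exact enumeration: Fisher's exact test 84.6%, continuity-corrected chi-square 84.0%. Stated: 84%.
- Pruritus, two-sample t-test: noncentrality 1.0 / (0.95 × √(2/20)) = 3.33 on 38 df, power 83.6%. Stated: 83%.

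Both agree, so the stated powers are used below.

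**2. Set-up.** Four normal test statistics: two primaries (P1, P2) and two main secondaries (S1, S2).

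- Critical values: 2.241 at 1.25% and 1.960 at 2.5%.
- Means for EU/RoW: 2.241 + z(0.84) = 3.236 for the primaries; 2.241 + z(0.83) = 3.196 for the secondaries. For the US these are exchanged.
- Correlation between doses: 0.5, from 1:1:1 allocation with a shared placebo (approximate for the binary endpoint).
- Correlation between endpoints: not in the protocol, so an assumption, varied from 0 to 0.9.

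**3. Rules compared.**

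- As written, both primaries succeed if P1 > 2.241 and P2 > 2.241.
- With transfer, they also succeed if P1 > 2.241, S1 > 2.241 and P2 > 1.960, or the same with the doses exchanged.

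Every rejection under the first rule is also a rejection under the second.

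**4. Power** (2 million simulated trials per setting, dose correlation 0.5).

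| Ordering | Endpoint correlation | Both primaries, as written | With transfer | Gain (points) |
|---|---|---|---|---|
| EU/RoW | 0 | 74.4% | 81.2% | 6.7 |
| EU/RoW | 0.5 | 74.3% | 81.1% | 6.8 |
| EU/RoW | 0.9 | 74.3% | 81.6% | 7.3 |
| US | 0 | 72.9% | 80.0% | 7.1 |
| US | 0.5 | 72.9% | 80.1% | 7.1 |
| US | 0.9 | 72.9% | 80.6% | 7.7 |

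Per-dose primary power for EU/RoW rises from 84.0% to about 87.4%. At-least-one-dose power is unchanged: 2 × 84.0 − 74.3 = 93.7% as written, and 2 × 87.4 − 81.1 = 93.7% with transfer.

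**5. Sensitivity.**

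- Patient-level simulation with Fisher and t-tests and a shared placebo arm (400,000 trials): EU/RoW from 74.4% to 82.1–82.5%; US from 73.7% to 81.2–81.5%.
- One dose weaker, with 70% power on each endpoint: 63.7% to 71.6% (+7.9). With 50%: 46.8% to 55.7% (+8.9).
- Bile acid test behaving like an uncorrected chi-square (per-dose power about 91%): EU/RoW gain about 5.5 points. That test does not match the stated 84%.

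**6. Error rate with transfer.**

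- Both primaries null: 2.30%.
- One dose null, the other at 84%/83%: the null dose's primary is rejected in 2.35%.
- One dose null, the other's main secondary almost certain to succeed: 2.49%.

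Strong control also follows from theory. This is a Bonferroni graphical procedure with starting weights of one half on each primary, and each rejected hypothesis passes its whole weight to one other.

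**The case against.** The strongest reply is that nothing here is wrong: the scheme controls the error rate as promised, and the stated powers were computed at the level it uses. That is true, and it limits the point to an efficiency gain.

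The protocol also sets no both-dose power target. It tests two doses because no single dose could be selected, and either dose may succeed alone. On that reading the relevant gain is about 3 points per dose, and nothing for at least one success. Those figures are right and belong beside the 7 points. But the objective names both doses, and the changed rule is never worse on any of these measures.

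Figure 2 might show a return arrow. If so, it would contradict the text, which fixes each primary at 0.0125, and the two would have to be reconciled.

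The SAP might add the transfer. However, the protocol does not leave the levels open, so such a SAP would depart from it.

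Finally, the planned primary analyses are a GLMM and an MMRM, and all figures rest on assumed effects. The exact gain is therefore uncertain; that the changed rule is at least as powerful is not.

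**Conclusion.** The point holds as an improvement available at no statistical cost, not as an error in the plan. As the text stands, both-dose primary power is about 73% to 74% under the protocol's assumptions and would be about 80% to 82% with the transfer. Per-dose primary power would rise by about 3 points, and the familywise error would stay within 2.5%. The 7-point figure assumes that both doses have the full planned effect, that the stated powers carry over to the mixed models, and a correlation of 0.5 between the dose comparisons. It changes little with the assumed endpoint correlation and grows somewhat if one dose is weaker. The reading rests on the text alone, because Figure 2 could not be seen.

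**What to change.** Add to section 11.2.2.1, in both the EU/RoW and US paragraphs:

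- A dose that is significant at one-sided 1.25% on its primary and on its main secondary passes that 1.25% to the other dose's primary, which is then tested at one-sided 2.5%.
- If that primary is significant, the second dose's main secondary is also tested at 2.5%.

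State the primary level as 1.25% initially, rising to 2.5% on transfer, so that it no longer reads as fixed at 0.0125. Check Figure 2 against the new text and draw an arrow from each dose's main secondary to the other dose's primary. When both primaries are won at 1.25%, the rule reduces to the Holm step already planned, so nothing else changes.

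The cost is two sentences, the adjusted level statement and a figure check. It needs no extra patients, visits or data and loses no error control. It must be in place before unblinding.

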**Figure 2 Bonferroni Holm Multiple Comparison Procedure**

In the US, for the primary efficacy variable pruritus score endpoint (change from baseline to Week 24 in observer-reported scratching), the null hypothesis will be tested against the alternative hypothesis ( $\alpha=0.0125$ , 1-sided).

The test will be performed at a Type I error rate of  $\leq 0.0125$  1-sided, as described above, based on the least squares means of the treatment difference in mean change.

To strictly control overall Type I error rate across the dose groups and also across the primary and the main secondary endpoint to a one-sided 2.5% level, a Bonferroni-based parallel gate-keeping procedure will be used. In this procedure the total significance level of 2.5% (1-sided) will be split equally between the dose groups. Only a dose group that is significant for the primary endpoint will be tested, at the nominal significance level of 1.25% (1-sided), for the main secondary endpoint (here the bile acid responder endpoint). If the previous step was not successful, the analysis of the following step will be considered descriptive. If the procedure reaches the secondary endpoint for both dose groups, these will be evaluated using the Bonferroni Holm procedure.

Other secondary and exploratory outcome variables shall provide supportive efficacy and safety information regarding the differences between the treatment groups. No adjustments will be performed for multiple dose comparisons when testing the other secondary and exploratory efficacy variables.

A more detailed statistical analysis plan (SAP) will be prepared and finalized before study data are locked and unblinded.

If not otherwise specified, the baseline value of a parameter is defined as the last assessment of that parameter on or prior to the first intake of study treatment date.

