## 9 ASSESSMENT OF EFFICACY

### 9.1 Efficacy Endpoints

#### 9.1.1 Primary Efficacy Endpoint

The primary efficacy endpoints are as follows:

- **European Union (EU) and rest of the world (RoW):** Proportion of patients experiencing at least a 70% reduction in fasting s-BA concentration from baseline to the end of treatment or reaching a level  $\leq 70$   $\mu\text{mol/L}$  compared to placebo after 24 weeks of treatment.

Fasting s-BA baseline will be calculated as the average of the value at randomization and the previous visit (Clinic Visit 2). The end value is the average of the values at Weeks 22 and 24 after the start of double-blind treatment.

- **United States (US):** Change in pruritus, as indexed by caregiver-reported observed scratching, from baseline to Week 24 as measured by the worst scratch of the Albireo ObsRO instrument ([Appendix 2](#)). Scores for the 14 days baseline and post-treatment intervals will be calculated by averaging the worst scratching scores from each day in the interval.

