#### 9.1.2 Secondary Efficacy Endpoint

Secondary efficacy endpoints include the following:

- **EU and RoW:** Change in pruritus, as indexed by caregiver-reported observed scratching, from baseline to Week 24 as measured by the worst scratch of the Albireo ObsRO instrument ([Appendix 2](#)). Scores for the 14 days baseline and post-treatment intervals will be calculated by averaging the worst scratching scores from each day in the interval.
- **US:** Proportion of patients experiencing at least a 70% reduction in fasting s-BA concentration from baseline to the end of treatment or reaching a level  $\leq 70$   $\mu\text{mol/L}$  compared to placebo after 24 weeks of treatment.
- **All Regions:**
  - All secondary endpoints are compared to placebo.
    - Change from baseline to Week 24 in fasting s-BA
    - Change from baseline to Week 24 in serum ALT concentration
    - Change in growth from baseline to Week 24, defined as the linear deficit (weight for age, and body mass index [BMI]) compared to the national growth curves (Z-score, standard deviation [SD] from P50)
    - Proportion of patients achieving meaningful reduction in caregiver-reported observed scratching at Week 24

- Change from baseline to Week 24 in sleep parameters measured with the Albireo PRO and ObsRO instruments
- Change from baseline to Week 24 in patient-reported itch severity as measured by the average daily score of the Albireo PRO instrument ([Appendix 2](#)); only patients  $\geq 8$  years of age will complete the Albireo PRO instrument
- Number of patients undergoing biliary diversion surgery or being listed for liver transplantation

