### 9.1.3 Exploratory Efficacy Endpoints

Exploratory efficacy endpoints are compared to placebo and include the following:

- Proportion of patients achieving meaningful reduction in patient-reported itch severity at Week 24
- Assessment of Global Symptom Relief at Weeks 4, 12, and 24 as measured by patient, caregiver, and clinician via the PGIC items ([Appendix 3](#))
- Change from baseline in fasting s-BA at Weeks 4 and 12
- Change in pruritus, as indexed by caregiver-reported observed scratching, from baseline to Weeks 4, 12, and 24 as measured by the worst scratch. Scores for the 7 worst scratching days of the last 14 days at baseline and post-treatment intervals will be selected
- Change from baseline in patient-reported itch severity and observer-reported scratching at Weeks 4 and 12
- Change from baseline to Week 24 in patient-reported and observer-reported night time itching and scratching severity scores, respectively
- Change from baseline to Week 24 in pooled pruritus score including observer-reported scratching for patients  $< 8$  years of age and patient-reported itch severity for patients  $\geq 8$  years of age
- Change from baseline to Week 24 in additional patient-reported and observer-reported sleep parameters (e.g., tiredness and number of awakenings)
- Change from baseline to Week 24 in PedsQL ([Appendix 4](#))
- Change from baseline in serum ALT concentration at Weeks 4 and 12
- Change from baseline in total bilirubin at Weeks 4, 12, and 24
- Change from baseline in AST at Weeks 4, 12, and 24
- Change from baseline for other biochemical markers and measures of bile acid synthesis (autotaxin, p-C4) at Week 24

- Change in pediatric end-stage liver disease/model for end-stage liver disease (PELD/MELD) score, AST to platelet ratio index (APRI) score, and Fib-4 score from baseline to Week 24
- Change from baseline to Week 24 in stage of liver fibrosis as assessed by Fibroscan® (where available)
- Liver-related mortality and liver decompensation events
- All-cause mortality

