### **9.2.2 Itching, Scratching and Sleep Score**

Itching, observed scratching, and sleep disturbance will be recorded twice each day via eDiary. Patients and/or caregivers will be instructed to complete the eDiary every day in the morning after the patient wakes and in the evening just before the patient goes to sleep throughout the study. Patients and caregivers will receive a formal training session during Visit 1.

The eDiary includes Albireo ObsRO and PRO items. Patients <8 years of age will not be asked to complete the Albireo PRO items; only the Albireo ObsRO will be completed by caregivers of patients in this age group. Older patients, 8 to 17 years of age, will complete the Albireo PRO items and the caregiver will complete the Albireo ObsRO items. The Albireo PRO items assess severity of itch, aspects of sleep disturbance (morning diary only), and tiredness. For patients 8 to 12 years of age, the caregiver will read the Albireo PRO items along with the child and record the child's response. A guide will be provided to the caregivers that provides standardized explanations of the Albireo PRO items, in case the patient is confused or requires clarification about the meaning of a question. The Albireo ObsRO items assess severity of observed scratching, aspects of observed sleep disturbance (morning diary only), and observed signs of tiredness (evening diary only). The Albireo ObsRO and PRO scratching and itch severity items use 0 to 4 response scales, where each response is distinguished by a unique facial expression, verbal anchor, number, and color code ([Appendix 2](#)).

A daily score for the Albireo ObsRO scratching item will be calculated by selecting the maximum scratching severity score from the 2 ratings for each day. A daily score will be considered missing if both of the daily assessments are missing. A 14-days score will be calculated by averaging the daily scratching scores. A 14-days score will be considered missing if >4 out of 7 days a week of data are missing. The same approach will be used to calculate a patient-reported itch severity score.

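### As written, the default baseline rule gives the eDiary sleep items a one-entry baseline, and evening-rated tiredness a post-dose one

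*Protocol*

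**What the plan says.** Section 11.2.2.1 (General Principles) closes with a general rule for anything that has no definition of its own: the baseline "is defined as the last assessment of that parameter on or prior to the first intake of study treatment date".

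Scratching has its own definition. Section 9.1.1 states: "Scores for the 14 days baseline and post-treatment intervals will be calculated by averaging the worst scratching scores from each day in the interval". Section 9.2.2 repeats it ("A 14-days score will be calculated by averaging the daily scratching scores") and adds one extension: "The same approach will be used to calculate a patient-reported itch severity score". Sleep and tiredness are not named there.

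The sleep endpoints are worded without an interval. Section 9.1.2 lists as secondary: "Change from baseline to Week 24 in sleep parameters measured with the Albireo PRO and ObsRO instruments". Section 9.1.3 lists additional sleep parameters as exploratory, with tiredness and number of awakenings as its examples.

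On timing, Section 9.2.2 places the sleep disturbance items, both patient- and observer-reported, in the morning diary only. For the observer instrument it then lists "observed signs of tiredness (evening diary only"). Patient-rated tiredness is not tied to either diary. The evening entry is made just before the patient goes to sleep. Under Sections 7.1.3.2 and 8.2, study drug is taken from Day 1, in the morning.

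Section 7.1.1 also mentions a 14-day diary window before randomization, but only for the eligibility calculation.

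**The concern.** A default of the last value before treatment suits a laboratory result drawn at a visit. It suits a twice-daily diary poorly, because the last value is one night or one day out of at least two weeks already recorded. Scratching and itch from the same device escape the default because they have their own 14-day rule; sleep does not.

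Two things follow. First, change from baseline in the sleep parameters carries the day-to-day noise of a single entry. Sleep disturbance is a stated secondary objective (Section 6.2) and there are only about 20 patients per arm, so precision is given up for no gain. Second, a rule set by date rather than by time of dose lets an assessment made after the first dose, but on the same day, count as baseline. For an item rated only in the evening this is the ordinary outcome of the rule, not a rare accident.

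**Working it through.** No figure in the protocol depends on this rule, so there is none to reproduce. The check applies the rule item by item and then illustrates its size.

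**Step 1: which rule applies, and which entry it selects.** Inputs: item timing (9.2.2), first dosing day (7.1.3.2), dose in the morning (8.2), default rule (11.2.2.1).

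| Diary item | Own interval? | Baseline as written | Before first dose? |
|---|---|---|---|
| Scratching (observer), itch severity (patient) | Yes, 14-day mean | 14-day mean | Default does not apply |
| Sleep disturbance (both instruments), morning only | No | Single Day 1 morning entry | Describes the night before the first dose |
| Tiredness (observer), evening only | No | Single Day 1 evening entry | No |
| Tiredness (patient), diary not restricted | No | Last entry dated Day 1 | No, if rated in the evening |

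The date wording does no harm to samples and questionnaires taken at Visit 3, because that visit is Day 0 and dosing starts on Day 1. The difficulty is specific to items that can be recorded on Day 1.

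**Step 2: illustration of the precision lost.** Let r be the correlation between two days' entries in the same patient. The protocol gives no value, so r is assumed. With the variance of one entry set to 1 and equal correlation between days, the variance of a 14-day mean is

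v14 = r + (1 − r)/14,

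and one entry has 1/v14 times that variance.

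- r = 0.9: v14 = 0.9 + 0.1/14 = 0.907; ratio 1.10
- r = 0.7: v14 = 0.7 + 0.3/14 = 0.721; ratio 1.39
- r = 0.5: v14 = 0.5 + 0.5/14 = 0.536; ratio 1.87
- r = 0.3: v14 = 0.3 + 0.7/14 = 0.350; ratio 2.86

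The reliability of one entry is r itself; that of the 14-day mean is r/v14. Over the same four values this is 0.90, 0.70, 0.50 and 0.30 for one entry, against 0.99, 0.97, 0.93 and 0.86 for the mean.

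These ratios concern the baseline value, not the change score. For the change, a second assumption is needed: the correlation c between a patient's underlying levels at baseline and Week 24. With a 14-day mean at Week 24 in both cases,

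- 14-day baseline: Var = 2·v14 − 2·c·r
- one-entry baseline: Var = 1 + v14 − 2·c·r

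At r = 0.9, c = 0.3: 1.367/1.274 = 1.07, so the SD of change is 1.04 times as large. At r = 0.3, c = 0.7: 0.93/0.28 = 3.32, so it is 1.82 times as large. These are the extremes over r from 0.3 to 0.9 and c from 0.3 to 0.7.

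**The case against.** The strongest reply is that this belongs to the SAP. The default applies only where nothing else is specified, Section 11.2.2.1 promises a more detailed SAP before lock and unblinding, and Section 11.2.3 plans a stand-alone SAP for the measurement properties of the diary items. Windows for supportive diary items are often set there. This stands in part: the SAP, which is not available here, may already override the rule. But the protocol is not silent. It states a rule, and an SAP that follows the protocol would carry it forward.

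It can also be said that a parameter may mean a derived period score rather than one entry. That reading works for scratching and itch, where a period score is defined. For sleep none is defined, so the only assessment the rule can select is an entry.

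The remaining objections limit the point, and they stand.

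- A reader might turn the extra variance into lost power. The documents do not support this. Section 11.2.2.6 analyses the sleep parameters descriptively, and the 1.25% one-sided tests cover only the bile acid and pruritus endpoints. The SD of 0.95 and the difference of 1.0 in Section 11.1 belong to the scratching score. Section 9.2.2 gives the 0 to 4 scale for scratching and itch only.
- A reader might assume that Week 24 is also one night. The default defines baseline only, and no passage makes the Week 24 sleep value a single entry.
- A reader might extend the post-dose problem to the secondary sleep endpoint as a whole. The sleep disturbance items are morning-only, so it cannot reach them.
- A reader might add night-time itch and scratching. These are itch and scratching severity scores, arguably covered by the 14-day approach in Section 9.2.2, so the default is not shown to apply to them.

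**Conclusion.** The point holds within limits. On the protocol's text, the sleep items take a one-entry baseline while scratching and itch from the same diary take a 14-day mean. Evening-only observer-rated tiredness takes a post-dose Day 1 baseline, as does patient-rated tiredness if it is rated in the evening.

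The first consequence is lost precision in a supportive, descriptively analysed secondary endpoint. Its size cannot be fixed from the protocol; 1.1 to 2.9 times the variance of a 14-day mean is an illustration that rests on the assumed day-to-day correlation. The second is an on-drug baseline, after one dose, for an exploratory item; any resulting bias cannot be estimated from the document. No confirmatory conclusion is touched: the bile acid and scratching endpoints have their own baselines. The whole point falls away if the SAP already sets a pre-dose interval for these items.

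**What to change.** Two changes, in the protocol or the SAP, before unblinding:

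1. In Section 9.2.2 (or the SAP), extend the 14-day approach to the sleep disturbance, tiredness and awakening items: baseline is the mean over the 14 days before the first dose, and the Week 24 value is the mean over the last 14 days of treatment.
2. In Section 11.2.2.1, define the default baseline as the last assessment before the first dose wherever the time of assessment is known, and keep the date wording only where it is not.

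The cost is two sentences. No new data are needed: the diary runs daily from Visit 1, and Section 7.1.1 already has the date and time of each dose reported in it, so a Day 1 entry can be placed before or after the first dose.
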